8.5 Visual Analog Scale (VAS)

VAS consists of three domains: daily functioning, anxiety/irritability, and irritability/language. For each of the domains, the parents/caregiver will mark on a visual line measuring 10 cm with one side marked "worst behavior" and the other side marked "best behavior." The parents/caregiver marks are measured in millimeter distance so that improvements or worsening of behavior over the treatment period can be evaluated.

Summary statistics (n, mean, standard deviation, minimum, median, and maximum) will be presented for the observed values and the change-from-baseline values to each posttreatment time point for each of the three domains for the ITT population and the completer population. In these displays, baseline will be defined as the last non-missing value obtained prior to first dose of study medication for Period 1, Day 1 predose.

The three domains of the VAS will each be analyzed using a mixed effect model. The change from baseline will be used in the model as the dependent variable. The model will include sequence, period, treatment, visit, predose baseline VAS score, baseline Stanford-Binet Full IQ score, and visit by treatment interaction as fixed effects, with subject within sequence as a random effect. This analysis will be done for both the ITT population and the completer population.

In addition, for Period 1 data only, the change-from-baseline to Week 12 will be analyzed using an analysis of covariance (ANCOVA) model with fixed terms for treatment, baseline VAS and baseline Stanford-Binet full IQ covariates for the ITT population for each domain.

The VAS results will be displayed in subject listings.

8.6 Aberrant Behavior Checklist (ABC)

ABC is a 58-item parent/caregiver rating scale used to assess behaviors across six dimensions or subscales: irritability, hyperactivity, lethargy/withdrawal, stereotypy, inappropriate speech and social avoidance. Items are evaluated on a four-point Likert scale ranging from 0 (not at all a problem) to 3 (the problem is severe in degree).

Summary statistics (n, mean, standard deviation, minimum, median, and maximum) will be presented for the observed values and the change-from-baseline values to each posttreatment time point for each of the six subscales for the ITT population and the completer population. In these displays, baseline will be defined as the last non-missing value obtained prior to first dose of study medication for Period 1, Day 1 predose.

For each subscale, the change-from-baseline to Week 12 will be analyzed using an analysis of covariance (ANCOVA) model which includes sequence, period, and treatment as fixed factors, subject within sequence as a random factor, and baseline ABC score and baseline Stanford-Binet full IQ covariates for the ITT population and the completer population.

Version 1.0 16 July 2020

In addition, for Period 1 data only, the change-from-baseline to Week 12 will be analyzed using an analysis of covariance (ANCOVA) model with fixed terms for treatment, baseline ABC and baseline Stanford-Binet full IQ covariates for the ITT population for each subscale.

All ABC assessments will be displayed in subject listings.

8.7 Anxiety Depression and Mood Scale (ADAMS)

ADAMS is a 28-item behavior-based informant instrument rated by the parent/caregiver and designed to assess anxiety, depression, and mood disorders in individuals with intellectual disability. Items are rated on a scale of 0 ("behavior has not occurred or is not a problem") to 3 ("behavior occurs a lot or is a severe problem"). The scale is composed of 5 factors which address: Manic/Hyperactive Behavior, Depressed Mood, Social Avoidance, General Anxiety and Obsessive/Compulsive Behavior.

Summary statistics (n, mean, standard deviation, minimum, median, and maximum) will be presented for the observed values and the change-from-baseline values to each posttreatment time point for each of the five factors for the ITT population and the completer population. In these displays, baseline will be defined as the last non-missing value obtained prior to first dose of study medication for Period 1, Day 1 predose.

For each factor, the change-from-baseline to Week 12 will be analyzed using an analysis of covariance (ANCOVA) model which includes sequence, period, and treatment as fixed factors, subject within sequence as a random factor, and baseline ADAMS score and baseline Stanford-Binet full IQ covariates for the ITT population and the completer population.

In addition, for Period 1 data only, the change-from-baseline to Week 12 will be analyzed using an analysis of covariance (ANCOVA) model with fixed terms for treatment, baseline ADAMS and baseline Stanford-Binet full IQ covariates for the ITT population for each factor.

All ADAMS results will be displayed in subject listings.

8.8 Event-Related Potentials (ERP)

Event-related Potentials (ERPs) enable extraction of neural responses associated with specific sensory, cognitive, or motor events from an overall EEG as cited in the protocol. Auditory stimuli are presented and EEG events assessed in relation to timing of the stimuli. For this study, an ERP protocol developed to measure auditory habituation to trains of repeated stimuli, resting state delta power, and oddball task responses in FXS will be used (Ethridge et al, 2017). This ERP protocol has shown feasibility and clinical validity based on comparison to sensory hypersensitivity on the Sensory Profile in FXS. The EEGs will be read by who developed the ERP protocol and has extensive experience in ERP evaluation.

The following parameters will be accessed:

- 1. Habituation
 - N1 amplitude to first paired stimulus

Version 1.0 16 July 2020

- FXS typically show increased N1 amplitude to auditory stimuli relative to typically developing controls. It is expected that the N1 amplitude will decrease as a sign of positive impact.
- N1 amplitude to second paired stimulus
 - FXS typically show increased N1 amplitude to auditory stimuli relative to typically developing controls, and in particular show a lack of reduction of N1 amplitude in response to repeated stimuli in a stimulus pair. It is expected that the N1 amplitude to the repeated stimulus will decrease as a sign of positive impact.
- N1 amplitude percent change between first and second paired stimulus
 - This is the amount of amplitude decrease (i.e. the amount of habituation) of the N1 ERP from first stimulus to second (repeated) stimulus in the pair, calculated as a ratio to control for individual differences in absolute ERP amplitude. It is expected that this ratio will increase as a sign of positive impact.
- 2. Oddball
 - P2 amplitude standard condition
 - FXS typically show increased P2 amplitude to auditory stimuli relative to typically developing controls. It is expected that P2 amplitude will decrease as a sign of positive impact.
 - P2 amplitude oddball condition
 - FXS typically show increased P2 amplitude to auditory stimuli relative to typically developing controls, but less differentiation between standard and oddball stimulus in amplitude. It is expected that P2 amplitude will decrease as a sign of positive impact.
 - P2 amplitude percent change between oddball and standard condition
 - FXS typically show increased P2 amplitude to auditory stimuli relative to typically developing controls, but less differentiation between standard and oddball stimulus in amplitude. Typically developing individuals show increased P2 amplitude to oddball stimuli relative to standard stimuli. It is expected that the ratio of P2 amplitude between standard and oddball stimuli in FXS will increase as a sign of positive impact.
- 3. Resting
 - Ratio of occipital alpha power during eyes closed condition during resting EEG
 - Typically developing individuals show increased occipital alpha power during eyes closed resting EEG compared to eyes open resting EEG, whereas FXS show less differentiation between the two conditions. It is expected that an increase in the ratio of eyes closed to eyes open alpha power in FXS as a sign of positive impact.

- Resting gamma power across whole head during eyes open condition
 - FXS typically show increased gamma power during rest compared to typically developing controls. It is expected that a decrease in gamma power as a sign of positive impact.

Summary statistics (n, mean, standard deviation, minimum, median, and maximum) will be presented for the above values and the change-from-baseline values to each posttreatment time point for each of the eight parameters for the ITT population and the completer population. In these displays, baseline will be defined as the last non-missing value obtained prior to first dose of study medication for Period 1, Day 1 predose.

For each parameter, the change-from-baseline to Week 12 will be analyzed using an analysis of covariance (ANCOVA) model which includes sequence, period, and treatment as fixed factors, subject within sequence as a random factor, and baseline ERP score and baseline Stanford-Binet full IQ covariates for the ITT population and the completer population.

In addition, for Period 1 data only, the change-from-baseline to Week 12 will be analyzed using an analysis of covariance (ANCOVA) model with fixed terms for treatment, baseline ERP and baseline Stanford-Binet full IQ covariates for the ITT population for each factor and the overall score.

All ERP results will be displayed in subject listings.

8.9 Eye Tracking

Eye tracking will be used to assess social gaze in the subjects. Testing will be conducted in a quiet room with the lights turned off. The eye tracker (Tobii) will be calibrated for each subject at the beginning of each session. Following calibration, subjects will view pictures shown on the screen. Each assessment begins with presentation of a scrambled face image for 1 s followed immediately by its matched face image for 3 s. An inter-trial interval containing a uniform grey screen is shown for 0.5, 1, or 2 s, randomly determined. The order of face presentation is pseudorandomized and each eye tracking session lasts approximately 6 min. Measurements will be the number of fixations and the proportion of looking time (%) for the following regions of interest: eyes, nose, mouth, and other. An increased in the number of fixations within the eye region and an increase in the proportion of looking time (%) within the eye region indicates an improvement within a subject.

Summary statistics (n, mean, standard deviation, minimum, median, and maximum) will be presented for the above values and the change-from-baseline values to each posttreatment time point for each of the above parameters for the ITT population and the completer population. In these displays, baseline will be defined as the last non-missing value obtained prior to first dose of study medication for Period 1, Day 1 predose.

For each parameter, the change-from-baseline to Week 12 will be analyzed using an analysis of covariance (ANCOVA) model which includes sequence, period, and treatment as fixed factors, subject within sequence as a random factor, and baseline eye tracking score and baseline Stanford-Binet full IQ covariates for the ITT population and the completer population.

In addition, for Period 1 data only, the change-from-baseline to Week 12 will be analyzed using an analysis of covariance (ANCOVA) model with fixed terms for treatment, baseline eye

Version 1.0 16 July 2020

tracking and baseline Stanford-Binet full IQ covariates for the ITT population for each parameter.

The data displays may be modified based on the actual data received for the analysis.

Eye tracking results will be displayed in subject listings.

8.10 Pharmacokinetics

The pharmacokinetic concentrations will be displayed in summary tables as well as in the subject listings.

8.11 Biomarkers (Pharmacodynamics)

A description of the biomarkers analysis is not included in this statistical analysis plan. The biomarker analysis, if conducted, will be exploratory and determined by the clinical results observed in the study.

9 SAFETY ANALYSES

9.1 Adverse Events

Adverse events will be coded using the Medical Dictionary for Regulatory Activities (MedDRA) coding system (using MedDRA version stated in Data Management Plan). An overall summary table will be presented by treatment group that summarizes all treatment-emergent adverse events, all serious treatment-emergent adverse events, all study drug-related treatment-emergent adverse events as assessed by PI, all study drug discontinuations due to treatment-emergent adverse events, number of deaths, and all severe treatment-emergent adverse events for the safety population. In addition, a frequency table will be presented by treatment group for all treatment-emergent adverse events by system organ class and preferred term for number and percentage of subjects:

- by maximum severity
- by relationship to study drug

An adverse event will be considered to be treatment-emergent for the treatment given in Period 1 if the event first appears after initial dosing in Period 1 or if it is a pre-existing condition that worsens following initial dosing through Period 2, Day 1. An adverse event will be considered to be treatment-emergent for the treatment given in Period 2 if the event first appears after Period 2, Day 1 or if it is a pre-existing condition worsens after Period 2, Day 1. Because the start time of adverse events is not collected on the case report form, it will be assumed that any TEAEs reported as starting on Period 2 Day 1 will be assigned to the treatment from Period 1. Any medical condition/event already present prior to the subject taking the first dose of study treatment will be reported in the medical history. Subject listings of all treatment-emergent adverse events will be provided.

In all displays, adverse events will be displayed by MedDRA System Organ Class and Preferred Terms, with subjects who have the same adverse event counted only once for that event and with subjects who have more than one adverse event within a System Organ Class counted only once

Version 1.0 16 July 2020

in that System Organ Class. An adverse event will be considered drug-related if, in the investigator's judgment, the event was related to treatment.

9.2 Laboratory Tests (Hematology, Serum Chemistry, and Urinalysis)

For hematology, chemistry, and urinalysis quantitative tests, summary statistics (n, mean, SD, minimum, median, and maximum) will be presented for the observed values at each time point by treatment group for the safety population. Summary statistics will also be presented for the change-from-baseline values to each post baseline time point. In these displays, baseline will be defined as the last non-missing value obtained prior to first dose of study medication for Period 1, Day 1 predose.

For all tests, results will be displayed in subject listings, with those values falling outside the laboratory reference range flagged. Laboratory reference ranges will be provided by the laboratory site(s) and will be included in an appendix of the clinical study report.

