6.5 Replacement of Subjects

Subjects who do not meet eligibility criteria at Baseline will not be randomized and will be considered screen failures. Subjects who withdraw from the study for any reason will not be replaced.

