11 PLANNED STATISTICAL METHODS

11.1 Sample Size

Given the exploratory nature of this study, a definitive sample size calculation is not possible. However, for the sake of providing an evaluation of the potential power to detect a meaningful difference between treatments, a crossover study having no carryover effects with 80% power, a 5% alpha level, and a common standard deviation of 3 units, a sample size of 30 evaluable patients (15 per sequence group) will allow detection of an effect size of approximately 2.25 units on the ABC Total Score outcome measure. If carryover effects or excessive dropouts allow only for a first Period analysis, a sample size of 15 per group during the first period would allow for detection of an effect size of 3.19 units.

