11.5 Safety Analysis

Safety analysis will be based on all subjects receiving at least one dose of study medication. Treatment emergent AEs will be summarized based on the frequency of AEs and their severity for all dosed subjects. Adverse Events (AEs), including clinically meaningful laboratory abnormalities and significant behavioral changes, will collected. AE severity and relatedness to treatment will be assessed. AEs will be tabulated for placebo and BPN14770 treatments using preferred terms and system organ classes. Summaries will also be provided by severity and relationship to treatment. Serious Adverse Events (SAEs) will be summarized separately, in a manner similar to that used for Adverse Events.

Overall safety and tolerability will be assessed by clinical and/or statistical review of all safety parameters including adverse experiences, laboratory values, vital signs, physical exams, and ECG data. General clinical and laboratory adverse events will be presented in frequency tables. Summary statistics (n, mean, SD, median, and range (minimum, maximum) will be tabulated for the observed values and the change (or percent change) from baseline for all continuous parameters for vital signs, ECG, and laboratory tests.

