2 STUDY OVERVIEW

This is a single center, Phase 2, randomized, double-blind, placebo-controlled, 2-period crossover study to obtain preliminary assessment of the effects of BPN14770 in subjects with Fragile X Syndrome. As schematic display of the study design is shown in Figure 1.

The study will consist of a Screening period of up to 28 days prior to initial study drug administration, followed by two 12-week double-blind treatment periods. The screening and the baseline visit for Period 1 may occur at the same time, provided the results of screening safety labs can be rapidly obtained. Subjects will be allowed to combine Period 1 Week 12 and Period 2 Day 1 visits. No washout period will be utilized between double-blind treatment periods; instead, efficacy and biomarker assessments during the second double-blind period (Period 2) will be obtained after a minimum of 6 weeks to allow for drug washout. A final follow-up phone contact for safety is planned one week after the conclusion of Period 2.

Eligible patients will be randomized in a blinded, balanced (1:1) fashion to receive either BPN14770 25 mg bid or matching placebo during Period 1, followed by the opposite treatment during Period 2.

Brief cognitive and behavioral assessments will be performed during each clinic visit. Safety and tolerability assessments throughout the study will include adverse event monitoring, ECGs, vital signs, blood chemistry, hematology, and urinalysis.

Pharmacokinetic samples will be collected at screening and at end of Periods 1 and 2 (Week 12) to confirm that study drug is present when expected and to estimate plasma exposure. Biomarker samples will be also collected at the time the pharmacokinetics samples are obtained.

[figure not shown]

Figure 1: Study Design Schematic

Study Duration

The total duration of the study of each subject will be up to 29 weeks, including a maximum of a 4-week screening period, two 12-week double-blind treatment periods, and a follow-up call approximately 1 week after last treatment.

Version 1.0 16 July 2020

Study Procedures

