9.3 Vital Signs

Summary statistics (n, mean, SD, minimum, median, and maximum) will be presented for the observed values for sitting systolic and diastolic blood pressure, pulse, respiration rate, and oral temperature at baseline and each post dose time point by treatment group for the safety population. Summary statistics will also be presented for the change-from-baseline values to each post baseline time point. In these displays, baseline will be defined as the last non-missing value obtained prior to first dose of study medication for Period 1, Day 1 predose.

All vital signs results will be displayed in subject listings.

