9.4 Electrocardiograms

Single ECG results will be collected at Baseline/Screening and at Week 6 and Week 12 of each study period. For the quantitative variables of QRS interval, PR interval, QT interval, QTcB interval, and Heart Rate, summary statistics (n, mean, SD, minimum, median, and maximum) will be presented for the observed values at Baseline/Screening and each post dose time point. Summary statistics will also be presented for change-from-baseline values to each post baseline time point. In these displays, baseline will be defined as the last non-missing value obtained prior to first dose of study medication for Period 1, Day 1 predose.

All ECG results will be displayed in subject listings.

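### SAP 9.2 to 9.4 plan no within-subject BPN14770-minus-placebo difference, with its confidence interval, for laboratory tests, vital signs or ECG

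*SAP*

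**What the plan says.** SAP 2 describes a "randomized, double-blind, placebo-controlled, 2-period crossover study to obtain preliminary assessment of the effects of BPN14770". Safety and tolerability is one of the three objectives (Protocol 4.4.1, SAP 3.1).

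For continuous safety data the SAP plans n, mean, SD, median and range:

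- Laboratory tests (9.2): these statistics "will be presented for the observed values at each time point by treatment group for the safety population", and the same for change from baseline.
- Vital signs (9.3): also by treatment group. "Summary statistics will also be presented for the change-from-baseline values to each post baseline time point".
- ECG (9.4): "Summary statistics will also be presented for change-from-baseline values to each post baseline time point". This section does not mention treatment group; that comes only from SAP 4.2, which shows results by treatment or by sequence where appropriate.

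In all three, baseline is the single value before the first dose of Period 1, and all results are also listed by subject. Protocol 11.5 plans frequency tables and summary statistics, and adds: "Overall safety and tolerability will be assessed by clinical and/or statistical review of all safety parameters". It names no method. Protocol 6.5 states: "Subjects who withdraw from the study for any reason will not be replaced". SAP 4.2 rules out imputation.

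A crossover model (fixed sequence, period and treatment, with a random subject effect nested in sequence) appears in SAP 8, for efficacy only.

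**The concern.** The design lets each subject serve as his own control, but the safety tables have the form that a parallel-group trial would use. Change from baseline does not fill the gap. Both periods are measured from the same pre-study value, so it shows change since entry, not drug against placebo.

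What is missing is a planned estimate of the drug effect together with its precision. A reader who has only the two columns must treat them as independent groups or pair the listings by hand. A modest shift is then harder to see, and harder to rule out, than the design allows.

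The protocol's background makes such a contrast useful. Protocol 4.3.1 reports, in dogs at 100 mg/kg, a QTc increase of about 30 msec with a 10 bpm rise in heart rate (females) and mild ALT elevation in two of eight animals. Protocol 4.3.2.2 reports ALT and AST increases as adverse events, each at 20%, in elderly subjects at 40 mg BID.

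**Working it through.** **Inputs.** From the documents: 30 subjects, 15 per sequence (Protocol 11.1), 1:1 allocation, no replacement of withdrawals, one common baseline. The documents give no SD, between-period correlation or dropout rate for any safety variable, so those below are assumptions.

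**The plan's own figure.** Protocol 11.1 assumes "80% power, a 5% alpha level, and a common standard deviation of 3 units" and states detectable efficacy differences of 2.25 units (crossover) and 3.19 units (Period 1 only). With a two-sided noncentral t on 28 df:

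- Crossover: SE = 3 × sqrt(2/30) = 0.775; detectable difference 2.248; power at 2.25 is 80.1%.
- Period 1 only: SE = 3 × sqrt(2/15) = 1.095; detectable difference 3.179; power at 3.19 is 80.3%.

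Both reproduce. They concern the ABC, not safety, and nothing here changes them.

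**Change from the common baseline.** Let B be the baseline, Y1 and Y2 the values on the two treatments, and let visits within a subject be exchangeable with variance s².

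- Var(Y1 − B) = Var(Y2 − B) = 2s²; Cov(Y1 − B, Y2 − B) = Var(B) = s². The correlation is s²/2s² = 0.5 for any s.
- Columns read as independent: SE = sqrt(2 × 2s²/n) = 2s/sqrt(n).
- Paired: the baseline cancels, so SE = sqrt(2s²/n) = 1.41s/sqrt(n).
- Ratio: 2/1.41 = 1.41.

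**Observed values, N = 30.** Half-widths of the 95% CI in SD units:

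- Independent columns: t(58) × sqrt(2/30) = 0.52 at any correlation.
- Paired: t(28) × sqrt(2(1 − rho)/30).

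| Assumed rho | Paired half-width | Relative to independent columns |
|---|---|---|
| 0 | 0.53 | 2% wider |
| 0.3 | 0.44 | 14% narrower |
| 0.5 | 0.37 | 28% narrower |
| 0.7 | 0.29 | 44% narrower |

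For illustration only, a QTc SD of 15 ms (range 10 to 20) with rho 0.5 gives 7.8 ms (5.2 to 10.3) for independent columns and 5.6 ms (3.7 to 7.5) paired.

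**What the columns do give.** With 15 per sequence and no missing data, the difference of column means equals the mean within-subject difference. Its SE depends on the covariance between periods, which the column SDs do not contain.

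**Dropout.** Suppose k subjects of one sequence miss Period 2. One column keeps a Period 2 share of 15/30; the other has (15 − k)/(30 − k). The column difference picks up k/(2(30 − k)) of any period effect: 1/58 = 1.7% for k = 1, 3/54 = 5.6% for k = 3, and 5/50 = 10% for k = 5.

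**ECG weeks.** SAP 9.4 places ECGs at Weeks 6 and 12 of each period. Protocol 10.3.3, 10.3.5 and the schedule in 16.1 place them at Weeks 2 and 12, and 10.3.4 lists none at Week 6. Protocol 8.8 speaks of every clinic visit except Week 1 but defers to the schedule. Week 12 is common to all.

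**The case against.** The strongest case against is that this is a small exploratory trial whose safety reporting is meant to be descriptive. The SAP delivers what Protocol 11.5 plans, no planned conclusion depends on a safety interval, and no passage is contradicted. Subject listings, with out-of-range laboratory values flagged, let a reviewer compare each subject with himself. Isolated elevations show better in the maximum and in those flags than in a mean difference. All of that stands, and it makes this an omission rather than an error. It does not answer the point, because an estimate with a confidence interval and no test is also descriptive, and hand-pairing from listings is not a planned analysis.

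A reader might infer more than the documents support:

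- *That the drug-placebo difference cannot be had at all.* With complete data the column means give it; only its precision is missing.
- *That dropout seriously confounds treatment with period.* The leakage is small and arises only if dropout differs between sequences.
- *That the protocol designates these variables as safety targets.* They are background findings. In dogs only ALT is reported, not AST, and the dose was above the 30 mg/kg NOAEL. The elderly cohorts showed no clinically significant effect on biochemistry or ECG.
- *That a contrast is equally clean at every visit.* There is no washout, and the plan holds back Period 2 efficacy assessments until Week 6, whereas laboratory tests are taken at Week 2.

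SAP 15.1 mentions table mockups that are not in the text reviewed, so the exact layout cannot be checked.

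**Conclusion.** The point holds as an inexpensive improvement that should be made. No drug-minus-placebo difference with its precision is specified for any laboratory, vital-sign or ECG variable, although the design supplies it and the SAP already uses a suitable model for efficacy.

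The loss is mainly one of precision. The factor of 1.41 for change scores rests on exchangeable visits. The 28% for observed values rests on a correlation of 0.5 and 30 complete subjects, and the gain disappears at correlation 0. The QTc widths are illustrations, not predictions. Period contamination is a minor addition. Nothing here shows a safety problem or alters the sample size statement.

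**What to change.** Keep the existing tables and listings, and make these changes:

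1. In SAP 9.2, 9.3 and 9.4, add for Week 12 the BPN14770-minus-placebo difference with a 95% CI for QTc, heart rate, systolic and diastolic blood pressure, ALT, AST and creatinine. Use fixed sequence, period and treatment, a random subject effect nested in sequence, and the variable's own baseline as covariate. The IQ covariate of 8.6 to 8.9 is not needed.
2. Label these results descriptive and give no P-values.
3. State in 9.4 that ECG results are shown by treatment group.
4. Reconcile the ECG visit weeks between SAP 9.4 and the protocol.
5. If a contrast is shown at an earlier week, add a note that there is no washout between periods.

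The cost is SAP wording and one small table per domain, from data already collected. The downside is more intervals, some of which will exclude zero by chance: with seven 95% intervals and no true effect, 7 × 0.05 = 0.35 are expected to do so. Hence the descriptive label.
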